### 7.2 Adverse Events

All AEs and SAEs occurring on Day 1 through the Day 29 ( $\pm$ 1 day)/Final Visit must be fully recorded in the subject's medical record and eCRF, and SAE form (if serious). AEs will be classified by SOC and PT using the most recent version of MedDRA.

#### 7.2.1 Treatment-emergent Adverse Events

For summary purposes, AEs will be classified as treatment-emergent AEs (TEAEs) or non-treatment-emergent AEs (non-TEAEs) depending on the comparison of AE onset date/time with the date of 1st study drug administration. A TEAE will be defined as an AE which occurred on or after the date of 1st study drug administration. For adverse events with incomplete start dates/times, the same imputation algorithm for missing or partial date/time information as described in Section 5.6 will be used for the determination of an AE being treatment emergent or not. Briefly, the unknown portions of an AE onset date/time will be imputed to the latest possible before being compared to the date of 1st study drug administration.

Non-TEAEs will be summarized separately from TEAEs by SOC and PT for each treatment group

and overall.

### **7.2.2 Adverse Event Severity**

Refer to the study protocol, Section 8.3.5.

### **7.2.3 Adverse Event Relationship to IP**

Refer to the study protocol, Section 8.3.4.

### **7.2.4 Serious Adverse Events**

Refer to the study protocol, Section 8.3.7.

### **7.2.5 Adverse Event Summaries**

All AEs (serious and non-serious) occurring after randomization and before the end of study, regardless of relationship to IP, will be included and classified by SOC and PT using MedDRA.

For TEAEs, the following will be summarized and presented for the SAF population:

- i. An overall summary of TEAEs, which includes:
  - a. the number and percentage of subjects experiencing a TEAE
  - b. the number and percentage of subjects experiencing a TEAE by strongest relationship to IP
  - c. the number and percentage of subjects experiencing a TEAE by greatest severity
  - d. the number and percentage of subjects experiencing a TEAE with Grade  $\geq 3$
  - e. the number and percentage of subjects experiencing a treatment-emergent SAE
  - f. the number and percentage of subjects experiencing a TEAE leading to death
  - g. the number and percentage of subjects experiencing a TEAE leading to study withdrawal
- ii. the number and percentage of subjects experiencing a TEAE by SOC and PT.
- iii. the number and percentage of subjects experiencing an adverse drug reaction (ADR; i.e., potentially related TEAE) by SOC and PT, where an ADR is defined as any TEAE with a causal relationship to IP assessed as 'Possibly Related' or 'Definitely Related'.
- iv. the number and percentage of subjects experiencing a TEAE by SOC, PT and the strongest relationship to IP
- v. the number and percentage of subjects experiencing a TEAE by SOC, PT and the greatest severity
- vi. the number and percentage of subjects experiencing a TEAE with Grade  $\geq 3$  by SOC and PT
- vii. the number and percentage of subjects experiencing an ADR with Grade  $\geq 3$  by SOC and PT
- viii. the number and percentage of subjects experiencing a treatment-emergent SAE by SOC

and PT

- ix. the number and percentage of subjects experiencing a potentially related treatment-emergent SAE by SOC and PT
- x. the number and percentage of subjects experiencing a TEAE leading to death by SOC and PT
- xi. the number and percentage of subjects experiencing a TEAE leading to study withdrawal by SOC and PT

In the overall summary of TEAEs table (i), besides tabulating the number and percentage of subjects, the total number of TEAE episodes will also be provided. If a subject has repeated episodes of a particular TEAE, all episodes will be counted in the summary table.

In the remaining summary tables, the incidence of TEAEs will be calculated by dividing the number of subjects who have experienced the event by the total number of subjects. Thus, the incidence of TEAEs is shown in terms of the total number of subjects and not in terms of the total number of episodes. If a subject has repeated episodes of a particular TEAE, only the most severe episode, or the episode with the strongest causal relationship to IP, will be counted in the summary tables.

A subject with more than one type of TEAE in a particular SOC or PT will be counted only once in the total of subjects experiencing TEAEs in that particular SOC or PT.

All occurrences of all AEs and SAEs will be listed for each subject, grouped by treatment group. The listing will contain the following information: treatment group, verbatim term, SOC, PT, severity (mild [Grade 1], moderate [Grade 2], severe [Grade 3-5]), relationship to IP, date/time and day of onset, date/time and day of resolution, action taken with regard to IP, whether additional non-drug or drug treatment was given to treat the adverse event, the outcome, whether the event was an SAE, whether it led to study withdrawal, whether it occurred during IP infusion, and whether it is a TEAE. Listings will be sorted by treatment group, subject identification number, onset date, SOC, and PT. If the onset date is completely missing, then these events will be presented first. If the onset date is missing a month or a day, then these events will be presented before any complete dates.

### 7.3 Clinical Laboratory Assessments

Clinical laboratory tests will be obtained at the time points presented in Appendix A. Continuous clinical laboratory values will be summarized by presenting descriptive statistics of raw data and change from baseline values at each time point for each treatment group, if feasible. If necessary, quantitative lab values reported in different units for the same lab parameter will be converted to the same units prior to being summarized. Qualitative results at each time point measured will be summarized by presenting the number and percentage of subjects for each category. Shift tables, based on the high/low flags, will also be summarized by treatment group at each visit for all laboratory tests with normal ranges, when available.

Laboratory parameter results from unscheduled visits will be excluded from table summaries but will be included in data listings. When there are repeat scheduled measurements for a given visit, only the last measurement will be used in the table summaries.

Listings will include flags for values outside of the reference ranges, when available, and clinical

significance if a laboratory result is deemed abnormal when applicable.

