
3. COVID-19 illness (symptoms) of any duration, including both of the following:
 
 a) Radiographic infiltrates by imaging (chest X-Ray, CT scan, etc.) and/or clinical assessment (evidence of rales/crackles on exam) with SpO2 <94% on room air b) Any One of the following related to COVID-19: i. Ferritin > 400ng/mL, ii. LDH > 300 U/L, iii. D-Dimers > reference range, or iv. C-reactive protein (CRP) > 40 mg/L 
4. Subject provides informed consent prior to initiation of any study procedures.
 
5. Female subjects of childbearing potential (and males with female partners of childbearing potential) must agree to use of acceptable contraception methods during study (e.g., oral, injectable, or implanted hormonal methods of contraception, placement of an intrauterine device or intrauterine system, condom or occlusive cap with spermicidal foam/gel/film/cream/suppository, male sterilization, or true abstinence*) throughout the study.
 
*True abstinence: When this is in line with the preferred and usual lifestyle of the subject. (Periodic abstinence [e.g., calendar, ovulation, symptothermal, post-ovulation methods], declaration of abstinence for the duration of a trial, and withdrawal are not acceptable methods of contraception.)
					

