
8. Subjects for whom there is limitation of therapeutic effort such as “Do not resuscitate” status Note: If the decision is made not to apply treatments or therapeutic procedures that will provide little benefit for the suffering or agony the subject is experiencing, such a subject would not be appropriate for participation in this study and should be excluded.
 
9. Currently participating in another interventional clinical trial with investigational medical product or device
 
10. Subjects previously requiring long-term oxygen therapy (home oxygen therapy)
 
11. History (within the last 2 years) of myocardial infarction, unstable angina, stroke or transient ischemic attacks, pulmonary embolism or deep venous thrombosis
 
12. Subject has medical condition (other than COVID-19) that is projected to limit lifespan to ≤ 1 year
 
13. Systolic blood pressure < 100 mm Hg or > 160 mm Hg (uncontrolled hypertension) at the time of Screening
 
14. Alanine aminotransferase (ALT) ≥ 2 times the upper limit of normal (ULN)
 
15. Any elevation of total bilirubin at the time of Screening
 
16. Estimated glomerular filtration rate (eGFR) < 45 mL/min (or subject is dependent on dialysis/renal replacement therapy) at the time of Screening
 
eGFR is calculated by the Cockcroft-Gault equation:
 
For men:
 $\frac{(140 - \text{age in years})(\text{body weight [kg]})}{(72)(\text{serum creatinine } \left[\frac{\text{mg}}{\text{dL}} \right])}$ 
For women:
 $\frac{0.85 \times (140 - \text{age in years})(\text{body weight [kg]})}{(72)(\text{serum creatinine } \left[\frac{\text{mg}}{\text{dL}} \right])}$ 
17. Hemoglobin < 10 g/dL at the time of Screening
 
18. Absolute neutrophil count $< 1000/\text{mm}^3$ at the time of Screening
 
19. Platelet count $< 75,000/\text{mm}^3$ at the time of Screening
 
20. Subject has history of drug or alcohol abuse within the past 24 months
 
21. Subject is unwilling to commit to follow-up visits
 
22. Known history of prothrombin gene mutation 20210, homozygous Factor V Leiden mutations, antithrombin III deficiency, protein C deficiency, protein S deficiency or antiphospholipid syndrome
																		

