10. Subjects previously requiring long-term oxygen therapy (home oxygen therapy)										
11. History (within the last 2 years) of myocardial infarction, unstable angina, stroke or transient ischemic attacks, pulmonary embolism or deep venous thrombosis										
12. Subject has medical condition (other than COVID-19) that is projected to limit lifespan to ≤ 1 year										
13. Systolic blood pressure < 100 mm Hg or > 160 mm Hg (uncontrolled hypertension) at the time of Screening										
14. Alanine aminotransferase (ALT) ≥ 2 times the upper limit of normal (ULN)										
15. Any elevation of total bilirubin at the time of Screening										
16. Estimated glomerular filtration rate (eGFR) < 45 mL/min (or subject is dependent on dialysis/renal replacement therapy) at the time of Screening										
eGFR is calculated by the Cockcroft-Gault equation: For men:										

GRIFOLS Bioscience Industrial Group	Number	BIG-CL-PRT-000019	Version	6.0	Status	Effective	Effective Date	08-Dec-2021
	GC2006-A Multicenter, Randomized, Open-label, Parallel Group Pilot Study to Evaluate the Safety and Efficacy of Prolastin®-C Liquid plus Standard Medical Treatment (SMT) versus SMT alone in Hospitalized Subjects with						Page	45 of 94

$$\frac{(140 - \text{age in years})(\text{body weight [kg]})}{(72)(\text{serum creatinine } \frac{\text{mg}}{\text{dL}})}$$

For women:

$$\frac{0.85 \times (140 - \text{age in years})(\text{body weight [kg]})}{(72)(\text{serum creatinine } \frac{\text{mg}}{\text{dL}})}$$

17. Hemoglobin < 10 g/dL at the time of Screening
18. Absolute neutrophil count < 1000/mm³ at the time of Screening
19. Platelet count < 75,000/mm³ at the time of Screening
20. Subject has history of drug or alcohol abuse within the past 24 months
21. Subject is unwilling to commit to follow-up visits
22. Known history of prothrombin gene mutation 20210, homozygous Factor V Leiden mutations, antithrombin III deficiency, protein C deficiency, protein S deficiency or antiphospholipid syndrome

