6.2 Prior and Concomitant Therapy

Concomitant medications must be recorded in the medical notes and in CRF, including the trade and generic names of the medication, the dose, the route of administration, and the duration of the medication (frequency). Concomitant prophylaxis for potential venous thrombosis or thromboembolism in hospitalized subjects with COVID-19 is supported within this study according to institutional standard practices.

Subjects should be managed according to standard of care for intercurrent illnesses, inclusive of influenza vaccine if appropriate depending on the clinical circumstance.

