7.2.9 Description of Laboratory Tests and Procedures

Table 7-1 Name, Description, and Location of Laboratory Tests and Procedures

provides a summary of the laboratory tests conducted for this study.

Table 7-1 Name, Description, and Location of Laboratory Tests and Procedures

Test Panel ^a		Description	Location
Effective Date	Page		
Hematology		Absolute neutrophil & lymphocyte count; Basic hematology: Hemoglobin, hematocrit, platelets, white blood cell (WBC) count with differential	Local
Chemistry		Creatinine, albumin, alanine aminotransferase (ALT), total bilirubin, lactate dehydrogenase (LDH)	Local
Markers of inflammation		C-reactive protein (CRP), D-dimer, ferritin	Local
Cytokine panel		Cytokine panel includes IL-1 β , IL-10, IL-6, IL-8, IL-2, interferon γ , and tumor necrosis factor- α (TNF- α). Note: serum samples must be stored at -70° C for later analysis at a reference laboratory.	Central
Quantitative measurement of SARS-CoV-2 viral load by NAT or PCR (RT-PCR)		Quantitative NAT or PCR (real-time RT-PCR) in respiratory samples (obtained via nasopharyngeal swab)	Central
Quantitative measurement of IgM and IgG antibodies to SARS-CoV-2		Quantitative IgM and IgG antibody levels by ELISA, IFA, or other assay methodology (if antibodies cannot be determined at the site store serum samples frozen at -70°C for later analysis at an external lab)	Central
AAT (activity & antigen)		Levels of alpha 1-PI (AAT) activity and antigen; both plasma (sodium citrate) and serum samples to be stored at -70° C for measurement of both antigenic content and functional activity (potency).	Store local/ Central analysis

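### Lab shift tables based only on high/low flags cannot separate further worsening in subjects already flagged abnormal at baseline; a graded worst-value shift by arm would

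*SAP*

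**What the plan says.** SAP section 7.3 states: "Shift tables, based on the high/low flags, will also be summarized by treatment group at each visit". It applies this "for all laboratory tests with normal ranges, when available". It makes no exception for any analyte, and the tables are by visit. The same section plans "descriptive statistics of raw data and change from baseline values at each time point for each treatment group", if feasible. Under SAP section 4 the statistics are n, mean, SD, median, minimum and maximum. Results from unscheduled visits are kept out of the tables, and where a scheduled visit has repeats only the last one is tabulated. Listings flag out-of-range values and, where applicable, clinical significance.

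The analytes concerned are ordinary study tests. Protocol section 7.2.9 puts "C-reactive protein (CRP), D-dimer, ferritin" in the inflammation panel and ALT and LDH in the chemistry panel, all run locally. Samples are scheduled at baseline and on Days 5, 15 and 29.

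Four entry rules matter:
- Inclusion 3b in the protocol synopsis: "Any One of the following related to COVID-19: i. Ferritin > 400ng/mL, ii. LDH > 300 U/L, iii. D-Dimers > reference range", with CRP above 40 mg/L as the fourth option.
- Exclusion 14 removes subjects only when ALT is at or above 2 times ULN.
- Exclusion 15 removes subjects with "Any elevation of total bilirubin at the time of Screening".
- Exclusions 17 and 19 remove subjects only when hemoglobin is below 10 g/dL or platelets are below 75,000/mm3.

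SAP section 8.1 reuses the Section 7 methods for the interim safety analysis.

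**The concern.** A low/normal/high scale has no category beyond high. A subject who starts there cannot move up, however large the later rise. Inclusion 3b and exclusion 14 admit subjects who start there on some analytes, and the same holds downward for hemoglobin and platelets. The by-arm shift tables could therefore look alike while more subjects in one arm have worsened substantially from an abnormal start. Both the interim and the final safety reviews would be reading tables that are blind to this.

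**Working it through.** The plan states no figure on this point, so there is nothing to reproduce. The check is logical, with arithmetic to show scale.

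**Step 1: which analytes can start flagged.**
- D-dimer: high by definition in a subject who qualifies on that criterion, if the qualifying value is also the baseline value.
- ALT: anything above 1 and below 2 times ULN is eligible and flagged high.
- LDH, ferritin, CRP: probably high in subjects who qualify on them. This assumes that the entry cut-offs (300 U/L, 400 ng/mL, 40 mg/L) lie above the local ULN; the documents give no local ranges.
- Hemoglobin, platelets: values below a local lower limit but above the exclusion cut-off are eligible and flagged low.
- Bilirubin: should not start high, given exclusion 15.
- Creatinine: exclusion 16 works through eGFR, and nothing in the documents shows how often creatinine starts high.

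**Step 2: what the table does with a rise.** Flag a value H if it exceeds 1 times ULN, otherwise N. The multiples are illustrative.

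| Baseline (x ULN) | Later value (x ULN) | Cell | Counted as a shift |
|---|---|---|---|
| 0.8 | 1.2 | N to H | yes |
| 0.8 | 20 | N to H | yes |
| 1.1 | 5 | H to H | no |
| 1.5 | 10 | H to H | no |
| 1.9 | 20 | H to H | no |

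A trivial crossing and a very large rise from normal share one cell. A large rise from an abnormal start is not counted as a shift at all.

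**Step 3: how much could be hidden.** Let h be the share flagged high at baseline on an analyte. If severe worsening is independent of the baseline flag (an assumption), the expected number hidden among 10 subjects who worsen is 10 x h:
- h = 10%: 1
- h = 30%: 3
- h = 50%: 5
- h = 80%: 8

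The documents do not give h for any analyte.

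**Step 4: what the change-from-baseline summary shows.** With about 100 subjects randomized 1:1, take 50 per arm. Each subject who goes from 1.9 to 10 times ULN adds (10 - 1.9)/50 = 0.162 times ULN to the arm's mean change. Three such subjects add 3 x 8.1/50 = 0.486 times ULN. The maximum shows the single worst value at that visit; neither statistic says how many subjects worsened.

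**Step 5: an extreme illustration.** Suppose 6 of 50 active subjects and 0 of 50 placebo subjects rise above 5 times ULN, and all six started between 1 and 2 times ULN. For these rises the shift table shows 0 against 0. The mean change would show something, because the six add more than 6 x (5 - 2)/50 = 0.36 times ULN to the active arm. The case is invented and deliberately the worst one.

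**The case against.** The best answer is that the shift table is only one part of the package. Protocol section 8.3.8 asks for clinically significant laboratory abnormalities to be reported as adverse events. SAP section 7.2.5 then tabulates events by greatest severity and at Grade 3 or above, by system organ class and preferred term. By-visit change with minimum and maximum, and flagged listings, cover more. With about 100 subjects and three scheduled post-baseline draws, those listings can be read. The four inflammation markers also enter the by-arm hyperinflammation table in SAP section 6.3. No commitment to graded lab shifts is broken, and the study is exploratory.

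All of this is right, and it limits the weight of the point. It does not close the gap. The adverse event route depends on the investigator's judgement and does not tabulate measured values. Listings give no count by arm. The hyperinflammation proportion is an efficacy composite that also requires a low lymphocyte count, so it does not isolate any analyte.

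A reader might infer more than the documents support:
- **That every subject starts high on these markers.** Inclusion 3b needs only one of the four and says nothing about ALT.
- **That severe hepatic, renal and coagulation changes as a whole would go unseen.** Bilirubin starts normal, creatinine is not shown to start high, and the other outputs carry part of the signal.
- **That the Grade 3-5 endpoint and the stopping thresholds cannot be reported.** Both are defined on adverse events, which have their own tables.
- **That D-dimer is the plan's laboratory monitor for thrombosis.** Protocol section 6.2 says "Concomitant prophylaxis for potential venous thrombosis or thromboembolism in hospitalized subjects with COVID-19 is supported within this study", and exclusions 11 and 22 concern thrombotic history and risk, but none of these mentions D-dimer. The protocol links D-dimer to mortality and hyperinflammation. A clinical thrombosis would itself be tabulated as an adverse event.
- **That a between-arm difference would be tested.** SAP section 7 plans no formal safety tests, so a p-value for the example in step 5 would have no place in the plan.

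**Conclusion.** The point holds as a modest reporting gap. For an analyte already flagged abnormal at baseline, further worsening stays in the same cell of the SAP 7.3 shift table, and no other planned table counts subjects by arm and by degree of measured worsening. ALT between 1 and 2 times ULN, and D-dimer in subjects who enter on it, follow from the entry criteria; LDH, ferritin and CRP rest on the assumption about local ULNs. Hemoglobin and platelets are exposed in the low direction. The share of subjects affected cannot be taken from the documents, and the hidden fractions in the working rest on the independence assumption. The rest of the safety package means that the signal is weakened rather than lost.

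**What to change.** In SAP section 7.3, keep the high/low shift and add one table per analyte: the shift from baseline to worst post-baseline category, by arm.
- Use CTCAE grade where one exists: ALT, creatinine, hemoglobin, platelets and neutrophils, with bilirubin optional. Name the CTCAE version, which the documents leave open.
- For D-dimer, use multiples of the local ULN. Include the cut at more than 2 times the upper limit that the hyperinflammation definition already uses.
- For this table only, include unscheduled results and all repeats. Under the present rules a peak seen at an unscheduled visit, or before the last repeat, would be left out and the worst value would be wrong.
- State that the table is also produced for the interim safety analysis in section 8.1.

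The cost is SAP wording, extra programming and somewhat larger tables. The values come from tests already scheduled, and the high/low flags already need the local reference ranges. No visit, sample, eligibility rule or clinical rule changes.

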
Respiratory samples for quantitative measurement of SARS-CoV-2 viral load by NAT or PCR (real-time RT-PCR) will be obtained on Day 1, and subsequently on Day 5 ± 1 day, Day 15 ± 1 day, and Day 29 ± 1 day (obtained via nasopharyngeal swab). The results of these samples are not necessary for continuing on study. Similarly, blood samples for quantitative measurement of IgM and IgG antibodies to SARS-CoV-2 via enzyme linked immunosorbent assay (ELISA), Indirect Fluorescent Antibody (IFA) or other assay methodology will be drawn at the same time points: Day 1, and subsequently on Day 5 ± 1 day, Day 15 ± 1 day, and Day 29 ± 1 day. The results of these samples are not necessary for continuing on study. These laboratory tests will be performed at a central/external lab.
 
Ferritin, D-dimer, CRP and Basic chemistry analytes (creatinine, albumin, alanine aminotransferase [ALT], total bilirubin, lactate dehydrogenase [LDH]) will be assessed on Day 1 and on Day 5 ± 1 day, Day 15 ± 1 day, and Day 29 ± 1 day. An estimated glomerular filtration rate (eGFR) will also be calculated at these time points using the Cockcroft-Gault formula.
 
Hematology (hemoglobin, hematocrit, platelet count, absolute neutrophil & lymphocyte count, leukocyte count with differential) will be assessed on Day 1, on Day 5 ± 1 day, Day 15 ± 1 day, and Day 29 ± 1 day. A cytokine panel will be performed on Day 1, and on Day 5 ± 1 day, Day 15 ± 1 day, and Day 29 ± 1 day. Cytokine panel includes IL-1β, IL-10, IL-6, IL-8 IL-2, interferon γ, and TNF-α. Note: serum samples must be stored at -70°C for later analysis at a reference laboratory. Levels of alpha 1-PI (AAT) activity and antigen will be evaluated on Day 1, on Day 8 ± 1 day, Day 15 ± 1 day, and Day 29 ± 1 day; both plasma (sodium citrate) and serum samples to be stored at -70°C for measurement of both antigenic content and functional activity (potency) (all samples are mandatory at all time points regardless of hospital discharge status, except for the Day 8 AAT activity and antigen which is not required if subjects are discharged from the hospital and no 2nd blinded study drug infusion is administered).
																		

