9.5 Procedure for Accounting for Missing, Unused, and Spurious Data

Handling of missing, unused and spurious data will be described in the SAP. All available efficacy and safety data will be included in data listings.

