#### **4.3 Assessment Windows**

Data will be summarized by nominal study visit recorded in the database.

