#### 4.6 Data Derivations and Transformations

The following derivations will be used in this study:

Study Day:

- Date of assessment – 1st date of study drug administration + 1 for assessments done on or after the 1st date of study drug administration
- Date of assessment – 1st date of study drug administration for assessments done before the 1st date of study drug administration

Baseline Observation: the last non-missing value prior to the 1st study drug administration.

Duration:

- Duration in days = end date – start date + 1
- Duration in minutes = end time in minutes – start time in minutes

Origin or Start Date for Time to Event Endpoints:

- Time to Clinical Response: date of 1st study drug administration
- Time to Hospital Discharge: date of 1st study drug administration
- Time to Sustained Normalization of Temperature: date of 1st study drug administration
- Time to Clinical Progression: date of 1st study drug administration

Event Date for Time to Clinical Response and time to sustained normalization of temperature:

- If a subject met the criteria for clinical response or sustained normalization of temperature at multiple assessments, the date of the first assessment meeting the definition of clinical response or sustained normalization of temperature will be used as the event date for deriving time to clinical response or sustained normalization of temperature.

Event Date for Time to Clinical Progression

- The event date will be the date of death, the start date of mechanical ventilation, or the date of ICU admission, whichever occurs first.

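### The last-value rule for repeated labs can drop an abnormal result from the by-visit shift tables, and no worst-post-baseline table is planned to show it

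*SAP*

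**What the plan says.** SAP 7.3 plans descriptive statistics by time point and, for tests with normal ranges, shift tables: "Shift tables, based on the high/low flags, will also be summarized by treatment group at each visit". Two rules decide which results enter these tables.

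- Repeats: "When there are repeat scheduled measurements for a given visit, only the last measurement will be used in the table summaries".
- Unscheduled results: "Laboratory parameter results from unscheduled visits will be excluded from table summaries but will be included in data listings".

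SAP 4.3 fixes how a result is tied to a visit: "Data will be summarized by nominal study visit recorded in the database". For the starting point of a shift, SAP 4.6 has "Baseline Observation: the last non-missing value prior to the" first dose.

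The laboratory schedule is sparse. The protocol synopsis says that the chemistry and inflammation markers "will be assessed on Day 1 and on Day 5", then on Days 15 and 29; haematology follows the same days. Each post-baseline time point has a window of one day either side, and no replicate draws are scheduled.

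For the listings, SAP 7.3 says "Listings will include flags for values outside of the reference ranges, when available", and Protocol 9.5 adds "All available efficacy and safety data will be included in data listings". Protocol 8.3.8 asks for a clinically significant laboratory abnormality to be reported as an adverse event.

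**The concern.** A shift table is there to show who moved out of the reference range, by arm. Keeping the latest of several values suits a by-visit mean, but it does not suit that purpose: when the order is abnormal and then normal, the subject is tabulated as normal. With only three post-baseline laboratory days, a subject has few other chances to show the abnormality in the tables.

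The adverse event tables follow the opposite principle. Under SAP 7.2.5, where a subject has repeated episodes of an event, the tables below the overall summary count the worst one (by severity or by relationship to study drug). The SAP gives no reason for treating laboratory values differently.

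SAP 8.1 carries the Section 7 methods into the interim safety analysis, so the same tables would inform that look as well as the final report. What is at stake is how complete the between-arm laboratory display is; no test or estimate of efficacy is involved.

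**Working it through.** The plan states no figure that depends on this rule, so there is nothing to reproduce. The check is to apply SAP 4.3 and the two rules of SAP 7.3 to each order of results that can occur.

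| Case | First result (scheduled visit) | Second result | Second result recorded as | By-visit shift table shows |
|---|---|---|---|---|
| 1 | abnormal | normal | same nominal visit | normal |
| 2 | abnormal | normal | unscheduled visit | abnormal |
| 3 | abnormal | abnormal, same direction | same nominal visit | abnormal |
| 4 | normal | abnormal | same nominal visit | abnormal |
| 5 | normal | abnormal | unscheduled visit | normal |

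- Case 1 is the loss described here. The abnormal value appears only in the flagged listing, and in the adverse event tables if it was judged clinically significant and reported.
- Case 2 is the reverse: the retest is excluded and the abnormal value stays.
- In cases 3 and 4 the last-value rule loses no abnormal class.
- Case 5 follows from the unscheduled-visit rule, not the last-value rule, but it has the same result: the abnormality is listed and not tabulated.

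Cases 1 and 2 can be the same clinical event. Which one applies depends on the nominal visit the site records, and the SAP does not say how a retest is to be classed. Repeats under one nominal visit are possible, because routine tests are run at the local hospital laboratory (Protocol Table 7-1) and Days 5, 15 and 29 have one-day windows.

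Size. For abnormal results at scheduled visits, the share lost through case 1 would be

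share lost = a × b × c,

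where a is the share of abnormal results that are retested, b the share of those retests that fall in a different class, and c the share of those recorded under the same nominal visit. The documents give none of the three, so the product cannot be evaluated.

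The weight of one affected subject can be stated. At the interim safety analysis, with about 25 per arm, one subject is 1/25 = 4% of an arm. At the end, with about 100/2 = 50 per arm, one subject is 1/50 = 2%. These are weights per subject and do not estimate how many would be affected.

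**The case against.** The strongest counter-argument is that the rule is limited to repeat scheduled measurements. A retest prompted by an abnormal result is not on the schedule, and if it is recorded as unscheduled the abnormal value stays in the shift table. This stands. A reader might infer that any abnormal result that triggers a retest vanishes from the tables; the documents do not support that. The loss needs a repeat under the same nominal visit that falls in a different high/low class.

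A reader might also want to attach a percentage to the under-count. Any such figure would rest on assumed retest and normalisation rates, and on every retest being filed under the scheduled visit. Nothing in the protocol or SAP anchors these.

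Second, the value is kept elsewhere: out-of-range results are flagged in the listings, all available safety data are listed, and clinically significant abnormalities should become adverse events. This also stands, and it means the value is missing from one type of table and not from the report. It does not fully replace the table, because listings give no counts by arm and the adverse event route depends on the investigator's judgement of clinical significance.

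Third, SAP 7 makes safety descriptive, with no formal testing, and the rule is the same in both arms. That is correct and keeps the point minor.

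Fourth, worst-value tables have a bias of their own: the more often a subject is tested, the greater the chance of an abnormal shift. That is fair and belongs in a footnote.

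**Conclusion.** The point holds in a limited form. The last-value rule governs the by-visit shift tables, and SAP 7.3 plans no worst-value or any-time post-baseline table to offset it. An abnormal value followed, under the same nominal visit, by a repeat in a different high/low class can therefore be absent from the between-arm laboratory tables, while remaining in the flagged listings and, if clinically significant, being reportable as an adverse event.

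The conclusion rests on two readings: that shift tables count as table summaries, and that a site may record a repeat under the scheduled visit. The size of any under-count cannot be estimated from the documents. The primary analysis, error rate and sample size are unaffected. This is a cheap improvement to the safety display, not a flaw that threatens the trial's conclusions.

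**What to change.** Keep the last-value rule for the by-visit descriptive statistics and the by-visit shift tables, and leave the baseline definition in SAP 4.6 as it is. Add to SAP 7.3 one shift table by treatment group, specified as follows:

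- from baseline (last pre-dose value) to the worst post-baseline value;
- shown separately for the lowest and the highest value where an analyte can be abnormal in both directions;
- using all valid scheduled, repeat and unscheduled results, and leaving out samples that the laboratory reported as invalid;
- with a footnote that subjects tested more often have more chance of an abnormal shift.

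Because the added table takes every valid result, it does not depend on whether a site files a retest under the scheduled visit or as unscheduled. That settles cases 1 and 2 alike and also picks up case 5.

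The cost is a few sentences in the SAP and one more table to program. The downside is that some transient abnormalities will be shown, and that the worst-value column depends partly on how often each subject was tested.
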